#### **5.5.4 Selection and Timing of Dose for Each Subject**

Subjects should take study drug as outlined in Section 5.5.1.

On dosing days that occur on study visit days, subjects should follow the regular dosing schedule (refer to Section 5.3.2.1 regarding Week 2 and Week 4 Visits).

Each subject's dosing schedule should be closely monitored by the site at each study visit by careful review of the subject's dosing diary. This will ensure that all subjects enrolled into the study maintain their original dosing schedule beginning with the first dose of study drug (Baseline/Day 1).

Upadacitinib/Placebo tablets (daily dosing):

- If a subject should forget to take his/her daily upadacitinib (or matching placebo) dose at his/her regularly scheduled dosing time, he/she should take the forgotten dose as soon as they remember the dose was missed as long as it is at least 10 hours before his/her next scheduled dose. If a subject only remembers the missed dose within 10 hours before next scheduled dose, the subject should skip the missed dose and take the next dose at the scheduled time.
- If the subject experiences a study drug interruption > 14 consecutive days during Period 1 or > 30 days during Period 2 (other than for reasons listed in Section 6.1.7), he/she should notify the Investigator, and the Investigator will determine if study drug should be restarted. If study drug treatment is interrupted or withdrawn in Periods 1 or 2, both daily and weekly study drug administration must be stopped. Period 2 may be unblinded after all subjects complete Period 1, at which time daily and weekly study drugs can be individually interrupted.

MTX/Placebo capsules or tablets (weekly dosing):

- Weekly MTX (or matching placebo) should be taken the same day and approximately the same time each week. If the subject should forget to take his/her oral MTX (or matching placebo) dose on his/her regularly scheduled dosing date, he/she should take the forgotten dose as soon as he/she remembers. If more than 72 hours has elapsed since the missed dose, the subject should contact the Investigator for further dosing instructions. The study drug can be taken with or without food.

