Subjects could be blindly switched from Upadacitinib monotherapy to the combination of upadacitinib + MTX at Week 26, or could have background csDMARD added/initiated after Week 26, depending upon the CDAI response and joint counts. For subjects rescued with blinded study drug MTX at Week 26, the exposure under upadacitinib monotherapy is censored prior to the day when blinded study drug MTX is initiated. For subjects not rescued with blinded study drug MTX at Week 26 but added/initiated csDMARD as a background therapy, the exposure under the monotherapy of upadacitinib is censored prior to the day when the first dose of csDMARD is initiated.

Starting with Amendment 5.01.01 (for Japan) and Amendment 6 (for global), subjects receiving upadacitinib 30 mg QD will be switched to receiving upadacitinib 15 mg QD. Exposure to upadacitinib 30 mg QD (Groups 4 and 5) will be censored prior to the day subject received the first dose of upadacitinib 15 mg QD, and subsequent exposure to upadacitinib 15 mg QD will be summarized under separate groups (Groups 6 and 7).

The duration of exposure to study drug will be summarized for each group as specified above, with the number of subjects, mean, standard deviation, median, minimum and maximum values. In addition, the number and percentage of subjects exposed to study drug will be summarized for the following cumulative duration intervals.

- ≥ 2 weeks
- ≥ 1 month
- ≥ 3 months
- ≥ 6 months
- ≥ 9 months
- ≥ 12 months
- ≥ 18 months
- ≥ 2 years
- ≥ 2.5 years
- ≥ 3 years
- ≥ 4 years

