1. MTX
2. Upadacitinib 15 mg QD
3. Upadacitinib 30 mg QD
4. MTX → Upadacitinib 15 mg QD + MTX
5. MTX → Upadacitinib 30 mg QD + MTX
6. Upadacitinib 15 mg QD → Upadacitinib 15 mg QD + MTX/csDMARD
7. Upadacitinib 30 mg QD → Upadacitinib 30 mg QD + MTX/csDMARD

For Japan sub-study, there are three additional exposure sequences:

8. Upadacitinib 7.5 mg QD
9. MTX → Upadacitinib 7.5 mg QD + MTX
10. Upadacitinib 7.5 mg QD → Upadacitinib 7.5 mg QD + MTX/csDMARD

Starting with Amendment 5.01.01 (for Japan) and Amendment 6 (for global), subjects receiving upadacitinib 30 mg QD will be switched to upadacitinib 15 mg QD. For these subjects, adverse events and exposure to upadacitinib 30 mg QD will be censored at the time of dose switch; subsequent adverse events and exposure starting the day of first dose

of upadacitinib 15 mg QD will be summarized under separate groups, as described in Section 8.1. Assessment of potentially clinically significant laboratory and vital sign values will be based on the same treatment exposure groups as for adverse events, as described above. For summary of mean change from baseline in laboratory values and vital signs, exposure sequences 3, 5 and 7 (i.e., subjects who switched from upadacitinib 30 mg QD to 15 mg QD) will be censored at the time of dose switch. Mean change from baseline for laboratory values and vital signs collected after dose switch will be summarized separately by visits post switch.

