10.3.3.2 Assessment of Potentially Clinical Significant Laboratory Values

Long-term laboratory data will be summarized based on the number and percentage of subjects meeting the criteria for potentially clinical significant laboratory values and by the actual treatment received at the time of the event occurrence. Starting with Amendment 5.01.01 (for Japan) and Amendment 6 (for global), subjects receiving upadacitinib 30 mg QD will be switched to upadacitinib 15 mg QD. The treatment exposure groups for summarizing potentially clinical significant laboratory values are the same as the ones for long-term AE analysis as described in Section 8.1 and Section 10.1.2.

In the evaluation of potentially clinically significant laboratory values, the baseline value will be determined by the last non-missing measurement recorded on or before the date of the first dose of study drug in the corresponding treatment group (which may be different than the first dose of study drug received in the study). For example, for a subject who started on MTX and switched to Upadacitinib 15 mg QD + MTX combo therapy, lab values under Upadacitinib 15 mg QD exposure would be evaluated against the baseline value defined as the last non-missing measurement recorded on or before the date of the

first dose of Upadacitinib 15 mg QD. For subjects who switched from upadacitinib 30 mg QD to upadacitinib 15 mg QD, lab values under upadacitinib 15 mg QD exposure would still be evaluated against the baseline defined based on the first dose of Upadacitinib 30 mg QD.

A listing of all subjects with any laboratory determination meeting OMERACT criteria of Grade 3 or 4 will be provided by Grade. For creatinine phosphokinase and creatinine, NCI CTC criteria will be used. Only subjects with worsening in grade compared to baseline grade will be captured. For each of these subjects, the whole course of the respective parameter will be listed.

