10.3.3.3 Assessment of Liver Elevations

The frequencies and percentages of subjects with post-baseline liver-specific function test values that meet the criteria of potential clinical interest (as described in Section 10.3.2.4) will be summarized by the actual treatment received at the time of the event occurrence. Starting with Amendment 5.01.01 (for Japan) and Amendment 6 (for global), subjects receiving upadacitinib 30 mg QD will be switched to upadacitinib 15 mg QD. The treatment exposure groups for summarizing liver elevations are the same as the ones for long-term AE analysis as described in Section 8.1 and Section 10.1.2.

A subject can be counted under different exposure groups if he/she switched study drug and experienced potentially clinical significant laboratory values under different exposure groups.

A listing of potentially clinically significant liver elevations based on criteria specified above will be provided. For each of these subjects, the whole course of the respective parameter will be listed.

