10.4.3 Analysis of Long Term Vital Sign

Analyses of mean change from baseline in continuous vital signs variables which are measured longitudinally will be performed by visits and by "as treated" exposure

sequences as described in Section 10.1.2. For each change from baseline analysis, the following summary statistics will be presented for each treatment group: sample size, baseline mean, visit mean, and the mean, standard deviation, and median of the changes from baseline.

Long Term Vital Sign will also be summarized based on the number and percentage of subjects meeting the criteria for potentially clinical significant vital sign values and by the actual treatment received at the time of the event occurrence. The treatment exposure groups are the same as the ones for long-term AE analysis as described in Section 8.1.

In the evaluation of potentially clinically significant vital sign values, the baseline value will be determined by the last non-missing measurement recorded on or before the date of the first dose of study drug in the corresponding treatment group, similarly as described in Section 10.3.3.2.

Starting with Amendment 5.01.01 (for Japan) and Amendment 6 (for global), subjects receiving upadacitinib 30 mg QD will be switched to upadacitinib 15 mg QD. Mean change from baseline in vital signs for subjects who switched from upadacitinib 30 mg QD to 15 mg QD will be censored at the time of dose switch, and mean change from baseline for values post switch will be summarized separately, as described in Section 10.1.2. The treatment exposure groups for summarizing potentially clinical significant vital sign values are the same as the ones for long-term AE analysis as described in Section 10.2.2 and Section 10.1.2. For the purpose of evaluating potentially clinical significant vital sign values, for subjects who switched from upadacitinib 30 mg QD to upadacitinib 15 mg QD, baseline is defined based on the first dose of Upadacitinib 30 mg QD, similarly as described in Section 10.3.3.2.

A listing of all subjects with any vital sign values meeting the criteria for potentially clinically significant vital signs will be provided. For each of these subjects, the whole course of the respective parameter will be listed.

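### In the long-term abnormal-value tables, a switch-visit sample that reflects 30 mg is counted under 15 mg when the first 15 mg tablet is taken later the same day

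*SAP*

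**What the plan says.** SAP 8.1 defines the exposure groups. Groups 4 and 5 hold 30 mg exposure (any use, and monotherapy). Groups 6 and 7 hold the later 15 mg exposure of the same subjects after the dose switch. On where the 30 mg groups end, 8.1 says that exposure "will be censored prior to the day subject received the first dose of upadacitinib 15 mg QD". On where the switched groups begin, SAP 10.1.2 says "subsequent adverse events and exposure starting the day of first dose" of 15 mg go to the separate groups.

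The same groups are then applied to measured values:

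- SAP 10.1.2: "Assessment of potentially clinically significant laboratory and vital sign values will be based on the same treatment exposure groups as for adverse events".
- SAP 10.3.3.2, PCS laboratory values: "The treatment exposure groups for summarizing potentially clinical significant laboratory values are the same as the ones for long-term AE analysis".
- SAP 10.3.3.3, liver tests: "The treatment exposure groups for summarizing liver elevations are the same as the ones for long-term AE analysis".
- SAP 10.4.3, vital signs: "The treatment exposure groups for summarizing potentially clinical significant vital sign values are the same as the ones for long-term AE analysis".

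Sections 10.3.3.2, 10.3.3.3 and 10.4.3 also say that results are summarised by the treatment the subject was actually receiving when the event occurred.

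For baselines, 10.3.3.2 uses "the last non-missing measurement recorded on or before the date of the first dose of study drug" in the corresponding group, so a value dated on the first-dose day counts as pre-dose. It makes an exception for the 30 mg to 15 mg switch, where the 30 mg baseline is kept.

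**The concern.** A whole-day boundary suits adverse events, whose onset can fall before or after a tablet on the same day. It does not suit a blood sample or blood pressure reading taken at the visit where the new tablets are handed out. Such a value describes the subject on 30 mg, but the day rule can place it in the 15 mg switched groups.

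Groups 6 and 7 were created to show what happens after the dose reduction. A misplaced value can make a subject a 15 mg case in a table that counts subjects. It also takes from the 30 mg groups their last on-dose value. Whether this happens depends on the hour at which the subject takes the tablet, not on exposure.

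**Working it through.** The plan gives no figure to reproduce on this point. The check applies its day rules to one visit.

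**Inputs**

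- Central laboratory tests, vital signs and dispensing fall at the same Period 2 visits (Protocol Appendix F).
- The dose switch is tied to a visit that varies by subject (SAP 7.0 and 9.1).
- Tablets on visit days: "On dosing days that occur on study visit days, subjects should follow the regular dosing schedule" (Protocol 5.5.4). A subject who usually takes the tablet after the time of the visit can therefore take the first 15 mg tablet on the visit date.
- That the sample precedes the first 15 mg tablet is inferred from dispensing at that visit; the protocol does not say so for Period 2. A sample soon after a single 15 mg tablet would still mainly reflect 30 mg.

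**Switch visit and sample on date D**

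| First 15 mg tablet | 30 mg group ends | Switched group starts | Sample dated D is counted in |
|---|---|---|---|
| later on D | D − 1 | D | Group 6 (and 7 if monotherapy) |
| D + 1 | D | D + 1 | Group 4 (and 5 if monotherapy) |

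The sample reflects 30 mg in both rows, yet the attribution differs. The principle of treatment at the time of the event would put both rows in Groups 4/5.

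**Is there protection elsewhere in the SAP?**

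- At the change from MTX to upadacitinib plus MTX, a first-dose-day value becomes the baseline for PCS laboratory values and so is not counted as an event on the new drug. At the 30 mg to 15 mg switch the 30 mg baseline is retained, so the same-day value is not absorbed.
- The only clock-time rule (SAP 10.2) concerns adverse events on the study drug start date. None covers samples at the dose switch.
- SAP Table 1, which covers laboratory values and vital signs, ends the Baseline window at Day 1 and starts Week 2 at Day 2. There, too, a first-dose-day value is treated as pre-dose.

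**Size**

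One visit at most is affected per switched subject. With k later on-drug visits, the misplaced visit is 1/(k + 1) of that subject's visits in the switched group. The documents do not give k. Visits run every 12 weeks to Week 240 and then Week 260, so:

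- assumed switch at Week 120: 10 visits (Weeks 132 to 240) + Week 260 = 11, and 1/12 = 8%;
- assumed switch at Week 204: Weeks 216, 228, 240 and 260 = 4, and 1/5 = 20%;
- k = 8: 1/9 = 11%; k = 1: 1/2 = 50%.

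The tables count subjects, so an illustration on that scale is closer to what would be seen. Assume 8 true post-switch draws, independent draws, an abnormality probability per draw of 0.5% on 15 mg and 1% on 30 mg, and a share f of subjects affected:

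- correct attribution: 1 − 0.995^8 = 3.93%;
- all affected (f = 1): 1 − 0.995^8 × 0.99 = 4.89%;
- half affected (f = 0.5): (3.93% + 4.89%)/2 = 4.41%;
- none affected (f = 0): 3.93%.

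The excess is f × 0.995^8 × 1% = f × 0.96 percentage points. None of these probabilities, nor f, is in the documents.

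**The case against.** The strongest reply is that the SAP already gives the right answer. Three sections attribute results by actual treatment at the time of the event, and a sample drawn before the first 15 mg tablet was drawn on 30 mg. The start-day wording is written for adverse events and exposure, not for samples. On this reading there is an unstated detail and no wrong rule.

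Part of this stands: the two statements conflict for a same-day sample, and a careful programmer might follow the principle. But 10.1.2 ties PCS laboratory and vital-sign values to the adverse-event groups immediately after giving their start day, and it refers back to that description. Those groups are defined by date. Programmed as written, the day rule decides.

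The limits on size also stand. A subject who has already taken that day's 30 mg tablet starts 15 mg the next day and is unaffected. For flagged subjects the SAP lists the whole course of the parameter, so a switch-day value can be traced.

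A reader might infer more than the documents support:

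- **That all long-term laboratory and vital-sign tables are affected.** The mean-change summaries follow a separate rule: only values obtained after the switch enter the post-switch summary (10.1.2, also 10.3.3.1 and 10.4.3).
- **That the liver table counts the last MTX-only value at Week 26 under upadacitinib plus MTX.** Section 10.3.3.3 is limited to post-baseline values but does not say which baseline applies after a change of treatment. If it is the treatment-specific baseline of 10.3.3.2, a first-dose-day value is excluded. This is an ambiguity, not a demonstrated error.
- **That the groups starting on 15 mg are contaminated.** The misplaced values go to the separately labelled Groups 6 and 7.

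**Conclusion.** The point holds for PCS laboratory values, liver elevations and PCS vital signs at the 30 mg to 15 mg switch. A stated date rule gives an attribution that contradicts the SAP's own principle, and the baseline rule that prevents this for PCS values at other treatment changes is switched off here.

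The consequence is modest: at most one visit per switched subject, in descriptive tables, and only where the tablet is taken after the visit on the same day. The percentages above show direction and order of size under stated assumptions; they do not estimate the actual error. The primary and Period 1 analyses were completed under SAP version 2.0 and are not touched. The conclusion rests on the inference that switch-visit samples precede the first new tablet.

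**What to change.** Add one rule to the PCS sentence of SAP 10.1.2, to 10.3.3.2, to 10.3.3.3 and to the PCS part of 10.4.3:

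*For the 30 mg to 15 mg switch, laboratory and vital-sign values dated on the day of the first 15 mg dose are attributed to the 30 mg group unless recorded times show they were collected after the first 15 mg tablet; attribution to the switched group otherwise starts the following day.*

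The clause on recorded times keeps a sample known to follow the tablet, such as an unscheduled draw, in the switched group.

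The cost is a sentence and a one-day change in the derivation; no new data are needed. There is a small downside. The laboratory and vital-sign boundary will differ by one day from the adverse-event boundary, so a switch-day abnormality that is also reported as an adverse event may appear under 30 mg in one table and 15 mg in another. A table footnote should say so.

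Separately, 10.3.3.3 should state which baseline defines post-baseline after a change of treatment.

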10.4 Analysis of Vital Signs

10.4.1 Variables and Criteria Defining Abnormality

Vital sign variables include sitting systolic blood pressure, sitting diastolic blood pressure, pulse rate, respiratory rate, body temperature, and weight. The criteria for potentially clinically significant vital sign findings are presented in [Table 14](#).

Table 14. Criteria for Potentially Clinically Significant Vital Sign Findings

Vital Sign	Category	Criteria for Potential Clinically Significant Vital Signs
Systolic blood pressure	Low	Value \leq 90 mmHg and decrease \geq 20 mmHg from Baseline
	High	Value \geq 160 mmHg and increase \geq 20 mmHg from Baseline
Diastolic blood pressure	Low	Value \leq 50 mmHg and decrease \geq 15 mmHg from Baseline
	High	Value \geq 105 mmHg and increase \geq 15 mmHg from Baseline
Weight	High	> 7% increase from baseline
	Low	> 7% decrease from baseline

10.4.2 Analysis of Vital Sign Prior to Protocol-Defined Treatment Switching at Week 26

Analyses of mean change from baseline in continuous vital sign variables which are measured longitudinally will be performed by visits and by the "as treated" treatment groups. For each change from baseline analysis, the following summary statistics will be presented for each treatment group: sample size, baseline mean, visit mean, and the mean, standard deviation, and median of the changes from baseline.

The number and percentage of subjects meeting the criteria for potentially clinically significant vital sign values will be summarized by "as treated" treatment group and overall.

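### After the 30 mg to 15 mg switch, the Group 6 and 7 laboratory and vital-sign percentages mix abnormalities carried over from 30 mg with new ones

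*SAP*

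**What the plan says.** SAP Section 10.3.3.2 summarises long-term potentially clinically significant laboratory values "by the actual treatment received at the time of the event occurrence". A value qualifies at Grade 3 or 4, with the restriction "Only subjects with worsening in grade compared to baseline grade will be captured". The general baseline in that section is the last value on or before "the date of the first dose of study drug in the corresponding treatment group", so a subject rescued from MTX to 15 mg plus MTX receives a new baseline at rescue.

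The dose switch is an explicit exception: values after the move from 30 mg to 15 mg "would still be evaluated against the baseline defined based on the first dose of Upadacitinib 30 mg QD". Section 10.4.3 repeats this for vital signs: "baseline is defined based on the first dose of Upadacitinib 30 mg QD, similarly as described in Section 10.3.3.2". Several vital-sign criteria in Table 14 are relative to baseline, for example weight "> 7% increase from baseline".

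Section 8.1 defines the exposure groups, and Section 10.1.2 applies them to laboratory and vital-sign abnormalities as well as to adverse events. Groups 4 and 5 hold 30 mg exposure, censored at the switch. Groups 6 and 7 hold 15 mg exposure after the switch and are labelled as switched from 30 mg. Group 2, the main 15 mg group, holds subjects who started on 15 mg or were rescued from MTX to it.

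**The concern.** The exposure group changes at the switch but the baseline does not. A Grade 3 value or a weight gain that developed on 30 mg and is still present at a 15 mg visit meets the criterion in both places.

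The table for Groups 6 and 7 is where a reader would look to see what happens after the dose reduction. As planned, it cannot show whether the abnormalities on 15 mg are new or were already there.

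Adverse events in the same groups follow a different logic. Sections 10.1.2 and 10.2.2 censor 30 mg events at the switch and send only later events to the post-switch groups. An adverse event that began on 30 mg and is still ongoing is counted once; a laboratory abnormality in the same position is counted twice.

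**Working it through.** There is no planned figure to reproduce. The check applies the SAP's own criteria to hypothetical courses, each with a value before 30 mg, the last value on 30 mg, and a value after the switch.

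**Criteria used**
- Hemoglobin (SAP Appendix A, K1): graded on the fall from pre-treatment; a fall of 2.1 to 2.9 g/dL is Grade 3.
- Lymphocytes, x1000 (Appendix A, K4): 1.5 to 1.9 is Grade 1 and 0.5 to 0.9 is Grade 3; the grade must be worse than at baseline.
- Weight (Table 14): change of more than 7% from baseline.
- Systolic pressure (Table 14): at least 160 mmHg with a rise of at least 20 mmHg.

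The worsening restriction stands in the listing paragraph of Section 10.3.3.2 and in the summary rule of Section 10.3.2.3. I take it to govern the long-term table too.

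| Course (before 30 mg / last on 30 mg / after switch) | Counted in Groups 4/5 | Counted in Groups 6/7, SAP baseline | Counted in Groups 6/7 if baseline were reset at the switch |
|---|---|---|---|
| Hemoglobin 13.0 / 10.5 / 10.5 | yes (fall 2.5) | yes (fall 2.5) | no (fall 0) |
| Hemoglobin 13.0 / 10.5 / 12.5 | yes (fall 2.5) | no (fall 0.5) | no |
| Hemoglobin 13.0 / 13.0 / 10.5 | no | yes (fall 2.5) | yes (fall 2.5) |
| Hemoglobin 13.0 / 11.5 / 10.5 | no (fall 1.5) | yes (fall 2.5) | no (fall 1.0) |
| Lymphocytes 1.6 / 0.8 / 0.8 | yes | yes | no |
| Lymphocytes 1.6 / 0.8 / 1.6 | yes | no | no |
| Lymphocytes 1.6 / 1.6 / 0.8 | no | yes | yes |
| Weight 70 / 76 / 76 kg | yes (6/70 = +8.6%) | yes (+8.6%) | no (0%) |
| Weight 70 / 76 / 72 kg | yes (+8.6%) | no (2/70 = +2.9%) | no |
| Weight 70 / 73 / 76 kg | no (3/70 = +4.3%) | yes (+8.6%) | no (3/73 = +4.1%) |
| Systolic 135 / 165 / 165 mmHg | yes (+30) | yes (+30) | no |
| Systolic 135 / 165 / 140 mmHg | yes (+30) | no | no |

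Three things follow.
1. Persisting abnormalities are counted in both places; resolved ones are not.
2. Under the SAP baseline, a carried-over case and a new case look the same in Groups 6 and 7 (compare hemoglobin 13.0/10.5/10.5 with 13.0/13.0/10.5).
3. Resetting the baseline is not a clean remedy. Cumulative change that first crosses the threshold after the switch (hemoglobin 13.0/11.5/10.5, weight 70/73/76 kg) would then be counted under neither dose.

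**Size.** Let f be the share of switchers who meet the criterion at the last pre-switch value and still meet it without worsening, and g the share who are new or worsened after the switch. The reported percentage is f + g, so it is at least f even when g = 0. The documents give neither f nor g.

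**Age of the baseline.** Protocol Section 5.5.5.2 says that all subjects had reached the end of Period 1 by September 2018. Counting back 48 weeks (336 days) from the end of that month puts the latest baseline for a subject randomised to 30 mg at about the end of October 2017. Amendment 6 is dated 16 December 2019, about 25 months later. Japan's Amendment 5.01.01 is dated 15 July 2019, about 20 months later. Slow change such as weight has time to build up before 15 mg starts.

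**The case against.** The strongest defence is that the rule is deliberate and coherent. A new drug resets the baseline; a lower dose of the same drug does not. Subjects rescued from MTX and subjects switched from 30 mg are both judged against the last value before their first upadacitinib dose. That stands: there is no contradiction within Section 10.3.3.2, and keeping the baseline preserves cumulative change that a reset would lose.

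Second, the SAP already plans whole-course listings for affected subjects (Sections 10.3.3.2 and 10.4.3) and a separate mean-change summary by visit after the switch (Section 10.1.2). This stands in part. The listings allow reconstruction by hand, but the mean change is still measured from baseline, and shift tables are specified only before Week 26 (Section 10.3.2.2). No planned summary table separates the cases.

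Third, Protocol Table 4 limits persistence for some parameters: confirmed neutrophils below 1000, white cells below 2000 or platelets below 50,000 per microlitre lead to interruption until recovery. This is true for those parameters. It does not reach lymphocytes of 0.5 to 0.9, hemoglobin falls of 2.1 to 2.9 g/dL, weight or blood pressure.

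A reader might also infer that the whole 15 mg safety profile is biased upward, or that everything that arose on 30 mg is recounted. The documents support neither. Switchers are kept out of Group 2, Groups 6 and 7 carry their history in their label, and a subject needs a qualifying value on 15 mg to count there.

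**Conclusion.** The point holds in a limited form. In Sections 10.3.3.2 and 10.4.3, Groups 6 and 7 combine abnormalities carried over from 30 mg with abnormalities new on 15 mg, and their percentages should not be read as onset on 15 mg. This rests on the stated baseline and attribution rules and on the long-term table using the Grade 3 or 4 and worsening criteria.

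The size is unknown. Any assumed f would simply return as the answer, so none is offered. The results for subjects who started on 15 mg or were rescued to it, the efficacy results and the completed Period 1 reporting are unaffected; SAP Section 11.1 confines this version to future long-term reporting. The matter concerns a descriptive table, but without a split that table leaves open whether abnormalities after the dose reduction are new.

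The liver table in Section 10.3.3.3 is outside the point. Its criteria are multiples of the upper limit of normal, so the choice of baseline does not alter them, and it already states "A subject can be counted under different exposure groups if he/she switched study drug and experienced potentially clinical significant laboratory values" under different groups.

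**What to change.** Keep the SAP's baseline and criteria. In Sections 10.3.3.2 and 10.4.3, split the Group 6 and 7 cases by the last value before the first 15 mg dose:

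- **(a) New or worsened after the switch:** criterion not met at that value, or a lower grade then. This includes cumulative change that first crosses the threshold after the switch.
- **(b) Carried over:** criterion already met at that value and persisting.

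State that only (a) is read as onset on 15 mg. In the worked courses, hemoglobin 13.0/10.5/10.5 and weight 70/76/76 kg fall in (b); hemoglobin 13.0/11.5/10.5 and weight 70/73/76 kg fall in (a), so nothing the SAP now captures is lost.

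Optionally, add change from the last pre-switch value to the post-switch mean-change summary. Leave Section 10.3.3.3 as it is.

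The cost is one derived flag and one extra row for the switched groups, with no new data collection.
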